### Measures

**Demographics.** Demographic information included age, date of birth, ethnicity, sex, height, weight, and concussion history.

**Insomnia Severity Index (ISI).** The ISI is widely used to measure insomnia severity and treatment response in sleep research. The ISI is a seven-item self-report questionnaire that assesses sleep onset latency, sleep efficiency, and functional impact from sleep issues. The sleep latency and efficiency items are rated on a 5-point Likert scale from 0 (*none*) to 4 (*very severe*). The remaining four items measure dissatisfaction, how noticeable sleep problems are to others, distress from sleep problems, and interference with daily functioning (all rated on 5-point Likert scales). Total scores on the ISI range from 0-28. Although the ISI was originally designed for adults, it has been shown to be valid in adolescent populations. In a clinical sample, an ISI score  $\geq 11$  has been shown to have 97% specificity and 100% specificity to detect insomnia. The current study used a cut score of  $\geq 12$  for eligibility to maximize the likelihood that participants had clinically significant insomnia symptoms. The ISI total score was the primary outcome measure for treatment response.

**Pittsburgh Sleep Quality Index (PSQI).** The PSQI is a widely used brief self-report measure of sleep quality aimed at examining the facets of sleep disturbance . It is composed of 19 items that measure sleep disruptions in the month prior to questionnaire completion. The PSQI contains seven subscales: subjective sleep quality, sleep latency, sleep duration, habitual sleep efficiency, sleep disturbances, use of sleep medications, and daytime dysfunction, which are combined into a total sleep quality score. The total PSQI raw score ranges from 0 to 21, with higher scores representing worse sleep disturbance; scores of greater than 5 indicate clinically significant sleep disruption . PSQI scores have adequate internal consistency . Additionally, the PSQI has shown validity for assessing sleep disturbances in adolescents following traumatic brain injury .

**Online Sleep Diary.** Participants completed an online sleep diary for the seven consecutive nights immediately following the completion of their questionnaire battery. Participants were asked to complete the sleep diary within an hour of waking up. The online sleep diary consisted of eight items assessing bedtime, duration of sleep initiation, night time waking, wake time, get-up time, nap time, and overall length and perceived quality of sleep. The perceived quality of sleep was collected by using a visual analog of a 5-point Likert scale ranging from 1 (*very poor*) to 5 (*very good*). Sleep diaries are a reliable estimate of sleep variables and considered a gold standard subjective sleep outcome . Sleep diaries have been used in other CBT-I studies with adolescents and have been shown to provide accurate sleep information in adolescent populations . Across each of the 7-day assessment periods, average total sleep time (TST), wake after sleep onset (WASO), sleep onset latency (SOL) and sleep efficiency (SE) were calculated.

*The 24-Hour Sleep Patterns Interview (SPI)* was used to ensure sleep diary compliance and consistency. The SPI is a telephone interview that asks participants questions about sleep patterns over the past 24 hours, including bedtime, night wakening (frequency and duration), and overall sleep quality. The 24-hour sleep patterns interview was developed to corroborate actigraphy data, but for the purposes of this study was used to ensure adherence and consistent reporting of sleep diary data. Participants received a phone call from a research assistant on day two and day five of the 7-day sleep diary period and were asked to verify their responses for the prior morning entry. This measure has been shown to be valid and feasible compared with a sleep diary .

**Dysfunctional Beliefs and Attitudes about Sleep (DBAS-16).** The DBAS was developed to identify unhelpful beliefs about sleep, and is composed of 16 items organized on an 11-point Likert scale that ranges from 0 (*strongly disagree*) to 10 (*strongly agree*). All item scores were summed to calculate a total raw score where higher scores indicate more negative beliefs and attitudes towards sleep. This scale identifies potential negative cognitions that can be held about sleep, such as the perceived consequences of insomnia, worry/helplessness about insomnia, general sleep expectations, and medications .

**Patient Reported Outcomes Measurement Information System (PROMIS®)**

**Anxiety.** The pediatric PROMIS® Anxiety questionnaire was developed by the National Institutes of Health (NIH) to evaluate symptoms of anxiety, such as feelings of fear, anxious misery, and hyperarousal in pediatric populations . The self-report version of the PROMIS® Anxiety questionnaire was included in this study. This 8-item measure queries anxiety symptom presentation based on the past seven days, with each item rated on a 5-point Likert scale ranging from 1 (*never*) to 5 (*almost always*). All item scores were summed to calculate a total raw score

where higher scores indicate more severe anxiety symptomology. The PROMIS® anxiety measure has been used in child, adolescent, and adult populations and has shown adequate or exceptional reliability .

**PROMIS® Depression.** The pediatric PROMIS® Depression questionnaire was developed by the NIH to evaluate symptoms of depression, such as feelings of hopelessness, helplessness, and worthlessness in pediatric populations . The self-report version of the PROMIS® Depression questionnaire was included in this study. This 8-item measure queries depression symptom presentation based on the past seven days, with each item rated on a 5-point Likert scale ranging from 1 (*never*) to 5 (*almost always*). All items were summed to calculate a total raw score where higher scores indicate more severe depressive mood symptomology. The PROMIS® depression measure has been used in child, adolescent, and adult populations and has shown adequate or exceptional reliability .

**Health and Behavior Inventory (HBI).** The Health and Behavior Inventory (HBI)  was used to measure the presence and severity of post-concussive symptoms based on adolescent self-report. The HBI measures the frequency of common somatic and cognitive post-concussive complaints and does not include any sleep-related items. The HBI is a 20-item questionnaire where symptoms are rated on a 4-point Likert scale ranging from 1 (*never*) to 4 (*often*) based on frequency over the past week. All items were summed to calculate a total raw score where higher scores indicate more severe post-concussive symptoms. The HBI was developed as a measure for both child and parent-proxy reports of post-concussive symptoms in children . The HBI has strong internal reliability  and is identified as a core common data element for pediatric brain injury research by the National Institute of Neurological Disorders and Stroke (NINDS) .

## Treatment

Participants in the treatment group received six weekly sessions of CBT-I. The protocol included psychoeducation about insomnia, relaxation strategies, instruction on sleep consolidation, stimulus control/sleep hygiene, cognitive restructuring, and problem solving/relapse prevention and mindfulness techniques. Sessions two through six began with a review of sleep diaries, calculation of sleep efficiency (SE), and troubleshooting of any problems encountered in home practice. This was followed by the introduction of new treatment components and a personal project for the next week. The protocol was based on CBT-I for adults and was adapted for use with adolescents with concussion by the research team, which included an experienced CBT-I therapist ([name]). The initial adaptation was piloted in a group form, but based on feedback CBT-I was delivered individually in this trial.

Manualized treatment was delivered by PhD students in clinical psychology, all of whom underwent a two-day training in delivery of CBT-I by the first author and were supervised weekly by a licensed PhD level clinical psychologist with experience in delivery of CBT-I and group supervision ([name]). A detailed description of the treatment by week is presented in Table 1. Average number of sessions attended was 4.9 (SD = 2.2), with nine of twelve (75%) participants attending all six sessions.

---

Insert Table 1 About Here

---

### Statistical Analysis

All analyses were conducted using SPSS 25.0^22. Baseline demographic and medical variables for the two conditions were compared using one-way ANOVAs and  $\chi^2$  tests. Intent-to-treat (ITT) analyses were conducted in line with CONSORT guidelines (i.e., all participants who

started the intervention were included) . ITT analyses were completed using maximum likelihood linear mixed model analyses. Between-group differences on primary and secondary outcome variables were also analyzed using linear mixed models. Linear mixed models are considered robust with respect to inclusion of participants with missing data in repeated measures research and are considered superior to traditional repeated measures ANOVA for longitudinal designs . Treatment group (CBT-I or TAU) was specified as the between-subjects factor, and time of measurement was the within-subjects factor. The effect of interest was the treatment group by time interaction coefficient. Models were tested to include a linear and quadratic time coefficient; in final models the quadratic time coefficient was removed for all analyses in which it was not significant. Multiple structures were tested for sigma, and the identity structure was chosen because it provided the best Schwarz's Bayesian Information Criterion (BIC) for each model. The treatment group variable was introduced as a dummy-coded variable with TAU as reference group. An  $\alpha$  of 0.05 was used to determine statistical significance. Effect sizes of 0.20, 0.50, and 0.80 were interpreted as indicating small, medium, and large effects, respectively. Standardized effect sizes for linear mixed models were derived by calculating standard deviation (SD)pooled =  $\sqrt{\frac{((\text{standard error } [se]_1 \cdot \sqrt{n_1})^2 \cdot (n_1 - 1) + (se_2 \cdot \sqrt{n_2})^2 \cdot (n_2 - 1))}{(n_1 + n_2 - 2)}}$  based on existing recommendations .

Other sleep data outcomes included change in PSQI, DBAS, and sleep diary measures. Most participants provided at least some sleep diary data. On average, participants provided data for 5.6 / 7 days at each assessment. Specifically, sleep diaries were completed by all 24 participants at baseline (mean days of completion = 6.0), by 19 participants at post-treatment (mean days of completion = 5.0), and by 20 participants at the four-week follow-up (mean days of completion = 5.7). All available sleep diary data were included in analyses.

Clinically significant change in ISI scores—the primary outcome variable—was also assessed in two ways. First, a variable indicating whether the ISI changed eight points or more was tested—a change of this magnitude is accepted as a meaningful change in CBT-I trials . Additionally, we calculated and analyzed the proportion of participants in each condition that reached a score below a cut-off of 8 (i.e., 0-7) on the ISI at each time point, indicative of “absence of insomnia” . To compare the proportion of participants who exhibited clinically significant change or reached a score below the cut-off, Fisher’s exact tests were used.

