A pilot randomized clinical trial of cognitive-behavioural therapy for insomnia in adolescents  
with persistent post-concussion symptoms

Date: September 19, 2018

Supplement 1.  
Trial Protocol.

Trial Design

This study involved a single-blind, parallel-group randomized control trial design comparing CBT-I and a treatment as usual (TAU) control group. Eligible participants were randomly assigned to either the active treatment (CBT-I) or the TAU control group using a gender blocked computer-based randomization tool (<https://www.randomizer.org/>). Participants who were randomized to the TAU condition were offered CBT-I after all follow-up measures were completed. Researchers administering the assessments were blinded to the randomization results. The trial followed and is reported according to CONSORT guidelines . The outcome measures chosen were informed by recommendations for assessing outcome in insomnia trials, including assessment of potential secondary gains associated with treatment . The study received was approved by the University of Calgary Conjoint Health Research Ethics Board (REB16-1166).

Participants and Procedures

Participants were recruited from the Alberta Children's Hospital (ACH) Brain Injury Clinic between October 2016 and August 2017. Adolescents were referred to the ACH Brain Injury Clinic based on persistent post-concussion symptoms. A total of 78 adolescents were approached, of whom 51 indicated interest in the study. Interested participants who could be contacted were screened for insomnia over the phone using the Insomnia Severity Index (ISI). If the potential participant received a score of  $\geq 12$  on the ISI, they were invited to attend a baseline session to determine eligibility. Of the participants who expressed interest in the study, 18 could not be reached for further screening and 9 did not meet the inclusion criteria. The final sample

consisted of 24 youth who were randomized to CBT-I (n=12) or TAU (n=12). Participant flow is presented in Figure 1.

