Inclusion criteria included: (1) 12-18 years of age; (2) diagnosed with a concussion by a nurse practitioner or physician at the ACH Complex Concussion Clinic (i.e., concussion was defined as an traumatic injury to the head, at least one reported symptom [e.g., dizziness, headache, nausea] at the time of the injury, and a Glasgow Coma Scale rating of  $\geq 13/15$  at 30 minutes after injury, or loss of consciousness  $< 30$  minutes, or post-traumatic amnesia  $< 24$  hours); (3) being at least 1 month but no more than 12 months post-injury to ensure symptoms were no longer acute, yet current and persistent; (4) reporting elevated symptoms of insomnia measured by an Insomnia Severity Index score of  $\geq 12$ ; and (5) ability to attend in-person treatment sessions. Exclusion criteria included: 1) moderate or severe TBI (i.e., Glasgow Coma scale rating of  $\leq 12$ , loss of consciousness exceeding 30 minutes, and/or post-traumatic amnesia exceeding 24 hours); and 2) visual, hearing, motor, and/or language deficits that would hinder the completion of questionnaires or engagement in CBT-I.

Assessments took approximately 45 minutes to complete and were conducted at baseline, post-treatment, and follow-up at four weeks after treatment. Assessments and treatment took place at the University of Calgary. In the first assessment at baseline, informed consent from the parent and informed assent from the adolescent were obtained in addition to baseline questionnaire data. If deemed eligible, participants were asked to fill out online sleep diaries for seven days. After the sleep diary was completed, participants were randomized to either CBT-I or TAU groups. If randomized to the CBT-I group, a study therapist contacted the participant and scheduled the first session. Seven weeks later, the post-treatment assessment was completed via online questionnaire and sleep diary. A third assessment was completed approximately four

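### The analysis called intent-to-treat is defined by starting the intervention, and the attendance figures show that at least one of the 12 CBT-I participants never did

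*Combined protocol and SAP*

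**What the plan says.** The Statistical Analysis section states that "Intent-to-treat (ITT) analyses were conducted in line with CONSORT guidelines" and then explains in parentheses that this means all participants who "started the intervention were included". It does not define starting, and does not say how the condition applies to the control arm.

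Four other places bear on it:

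- **Order of events (Participants and Procedures).** Randomisation follows the baseline diary. Only then: "If randomized to the CBT-I group, a study therapist contacted the participant and scheduled the first session".
- **Control arm (Trial Design).** "Participants who were randomized to the TAU condition were offered CBT-I after all follow-up measures were completed".
- **Attendance (Treatment).** "Average number of sessions attended was 4.9 (SD = 2.2), with nine of twelve (75%) participants attending all six sessions".
- **Data used (Statistical Analysis, on diaries and clinically significant change).** All 24 participants gave baseline diaries, 19 gave them post-treatment and 20 at follow-up, and "All available sleep diary data were included in analyses". The Fisher tests on ISI response and remission are described without naming an analysis set.

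**The concern.** Intent-to-treat means everyone randomised, analysed in the arm assigned. A set conditioned on starting treatment is at best a modified ITT set. Here the condition is also one-sided. There is a gap between randomisation and session 1 in which a CBT-I participant can drop away, while a TAU participant has nothing to start until the outcomes are complete. Read literally for both arms, the rule would leave no control group; read in the only workable way, it can exclude CBT-I participants alone.

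What is at stake is whether the primary ISI comparison is as randomised. If a CBT-I participant who never attended was left out, the protection of randomisation is lost for that comparison. If that person was followed and did not improve, the omission favours CBT-I. With 12 per arm, one person is 8% of an arm.

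**Working it through.** **1. Does anyone fail the condition?** Inputs, all from the Treatment section: 12 CBT-I participants, a maximum of six sessions, nine attending all six, mean 4.9, SD 2.2. Assumption: attendance is counted in whole sessions, so each of the other three attended 0 to 5.

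- *Total.* 58/12 = 4.83, 59/12 = 4.92, 60/12 = 5.00. Only 59 rounds to 4.9.
- *Remainder.* Nine completers account for 9 × 6 = 54, so the other three attended 59 − 54 = 5 sessions between them.
- *SD.* The sum of squared deviations is 9 × 36 + (a² + b² + c²) − 59²/12 = 324 + (a² + b² + c²) − 290.083, where a, b, c are the three remaining counts. Divide by 11 (n−1) or 12 (n) and take the square root.

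| Split of the 5 sessions | Sum of squared deviations | SD, n−1 | SD, n |
|---|---|---|---|
| 0, 0, 5 | 58.917 | 2.314 | **2.216** |
| 0, 1, 4 | 50.917 | **2.151** | 2.060 |
| 0, 2, 3 | 46.917 | 2.065 | 1.977 |
| 1, 1, 3 | 44.917 | 2.021 | 1.935 |
| 1, 2, 2 | 42.917 | 1.975 | 1.891 |

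The reported 2.2 is reproduced by (0, 1, 4) with the usual n−1 divisor, and by (0, 0, 5) with the n divisor. Both contain a zero. Without a zero attender the SD cannot exceed 2.02, so the conclusion does not hang on how 2.151 rounds. At least one CBT-I participant attended no session.

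**2. Size of the set under the stated rule.** Taking starting to mean attending at least one session, and applying the rule in CBT-I only, the set is 11 vs 12 (1/12 = 8% of CBT-I removed) with the n−1 SD, or 10 vs 12 (2/12 = 17%) with the n divisor. As randomised it is 12 vs 12.

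**3. Effect on the group-by-time slope.** The documents give no ISI results, so this is an illustration. Assumed: three visits, the other 11 CBT-I participants change by −4 ISI points per visit relative to TAU, one non-starter changes as TAU does, residual SD 3. The expected coefficient was computed with a random intercept (SD 3) and with independent errors only.

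| Non-starter's data | Slope, kept | Slope, dropped | Dropped / kept |
|---|---|---|---|
| All three visits | −4 × 11/12 = −3.667 | −4.000 | 12/11 = 1.091 (both models) |
| Baseline and post-treatment | −3.939 (random intercept); −3.995 (independent) | −4.000 | 1.016; 1.001 |
| Baseline only | −4.000 | −4.000 | 1.000 |

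In the baseline-only case, a baseline ISI 3 points above the arm mean gives ratios of 0.985 (random intercept) and 0.969 (independent); 3 points below gives 1.016 and 1.033.

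**4. Effect on the Fisher tests.** This applies only if the same set was used for them and the non-starter had a post-baseline ISI and did not respond. Illustrative counts, two-sided:

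- 4/12 vs 0/12, p = 0.093, becomes 4/11 vs 0/12, p = 0.037.
- 7/12 vs 2/12, p = 0.089, becomes 7/11 vs 2/12, p = 0.036.

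These are chosen cases. With 12 per arm and at least one CBT-I non-responder there are 12 × 13 = 156 tables; removing one CBT-I non-responder carries 8 of them across 0.05. That counts tables and is not a probability.

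**The case against.** The best defence is that the parenthesis is loose wording and was never the operating rule. Applied literally it deletes the control group, so nobody can have applied it literally. The one-sided reading is literal for CBT-I and lenient for TAU, and the document never states that hybrid. The authors may only have meant that the analysis was not confined to completers.

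Other text leans the same way. All 24 randomised youth are called the final sample. The attendance summary uses a denominator of twelve, so the person with no sessions is still counted in the arm. All 24 gave baseline diaries and all available diary data were used. Mixed models are justified by their handling of missing data. Figure 1, the participant flow, is not available to this review and may give the analysed numbers.

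The likely effect is also small. The 9% slope figure needs a never-attender who completed every assessment and changed exactly as TAU did, and one who improved more than the attenders would reverse the direction.

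Much of this stands: no exclusion is shown, and an effect on the results is only a possibility. It does not rescue the definition. The diary statement does not cover the ISI models or the Fisher tests, and attendance denominators do not say who entered a model. A reader following the stated rule, with a non-starter in the arm, reaches a set that is not as randomised.

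**Conclusion.** The concern holds. The stated definition is not intent-to-treat and in practice can act only on CBT-I. The plan's own attendance figures require at least one participant who fails it, given whole-session counts and starting taken as attending a session.

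If all 24 were analysed, the label is right and only the explanatory wording is wrong. If the rule was applied to one non-starter, the slope is affected by 0% to 9% under the assumptions above, with about 3% either way from an unusual baseline score, and a Fisher result near the threshold could change. Confidence is high about the wording and the non-starter; nothing here shows that the reported results are wrong. It should be corrected because it concerns the set for the primary outcome.

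**What to change.** Replace the parenthetical definition with one sentence: the ITT set is all 24 randomised participants, analysed in the assigned arm whatever the number of sessions attended, for the mixed models and the Fisher tests alike. State the analysed N per arm for each model and each Fisher test.

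Re-run only if someone was left out. In most of the scenarios above the estimate would then be unchanged or slightly less favourable to CBT-I. If a set restricted to those who started is also reported, label it modified ITT and present it as a sensitivity analysis. Counting a missing ISI as non-response in the Fisher tests is an optional further sensitivity analysis; the ITT definition does not require it.

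The cost is a sentence and a few counts. No new data are needed, since baseline questionnaires were collected before randomisation and all 24 have baseline diaries.

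### Maximum likelihood with 12 per arm and no stated small-sample correction makes the mixed-model tests slightly too liberal if within-person correlation is modelled; the covariance model must be settled first

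*Combined protocol and SAP*

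**What the plan says.** All of this is in the Statistical Analysis section of the combined protocol and SAP, except the design figures.

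- Estimator: "ITT analyses were completed using maximum likelihood linear mixed model analyses". REML is not mentioned, and no degrees-of-freedom method or small-sample correction is given.
- Target: "The effect of interest was the treatment group by time interaction coefficient". The significance threshold is an alpha "of 0.05 was used to determine statistical significance"; sidedness is not stated.
- Time: "Models were tested to include a linear and quadratic time coefficient", and "in final models the quadratic time coefficient was removed for all analyses in which it was not significant".
- Covariance: several structures were tried for sigma and identity was kept on BIC. The text does not say whether sigma is the residual or the random-effects matrix, or whether a subject random effect was fitted.
- Effect size: "Standardized effect sizes for linear mixed models were derived by calculating standard deviation" from arm-specific standard errors, each multiplied by the square root of the arm size and then pooled. Which standard errors these are is not stated.
- Design (Participants and Procedures): 24 randomized, 12 per arm, with assessments "conducted at baseline, post-treatment, and follow-up at four weeks after treatment".

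**The concern.** ML variance estimates do not allow for the fixed effects estimated from the same data, so they are biased downward. The bias is negligible in a large trial but not with 24 participants. Where it operates, the standard error of the group-by-time coefficient is too small and the test rejects more often than the nominal 5%. Because the plan rebuilds the SD of its effect size from standard errors, the same shortfall can enter the denominator of each standardized effect. In a pilot, those effect sizes are likely to inform the planning of a later trial. The primary ISI analysis and the secondary outcomes use the same method.

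**Working it through.** The plan gives no figure to reproduce, so the check derives the size of the bias.

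**Inputs from the document.** 24 participants, 12 per arm; 3 occasions, so at most 24 × 3 = 72 observations; alpha 0.05. For a missing-data case, the sleep-diary counts are used: 24 + 19 + 20 = 63 observations.

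**Assumptions.** Two-sided test; normal data; within-person correlation 0.3, 0.5 or 0.7; if quadratic time is kept, its interaction with group is kept too; missingness as in the diaries (no ISI counts are given).

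**1. Correlation modelled, closed form.** Let m be the ML divisor and r the REML degrees of freedom.

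- SE ratio (ML/REML) = √(r/m)
- Type I error = P(|t_r| > t_{0.975,m} × √(r/m))

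With a random intercept, m = 72 − 24 = 48. Linear time and its interaction use 2, so r = 46; adding the quadratic pair gives r = 44. With 63 observations, m is approximately 63 − 24 = 39, and r is 37 or 35. With a random slope or unstructured covariance, m = 24 and r = 24 − 2 = 22.

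| Model | r, m | SE ratio | Type I, t | Type I, z |
|---|---|---|---|---|
| Random intercept, linear, 72 obs | 46, 48 | 0.979 | 5.5% | 6.1% |
| Random intercept, quadratic, 72 obs | 44, 48 | 0.957 | 6.1% | 6.7% |
| Random intercept, linear, 63 obs | 37, 39 | 0.974 | 5.6% | 6.4% |
| Random intercept, quadratic, 63 obs | 35, 39 | 0.947 | 6.4% | 7.2% |
| Random slope or unstructured, complete | 22, 24 | 0.957 | 6.1% | 7.4% |

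Worked example, first row: √(46/48) = 0.979; t_{0.975,48} = 2.011; 2.011 × 0.979 = 1.968; P(|t_46| > 1.968) = 5.5%.

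**2. Simulation check.** There were 20,000 null data sets per scenario, with times at 0, 7 and 11 weeks and random-intercept fits. ML with Satterthwaite t gave 5.5–5.9% (linear) and 5.9–6.6% (quadratic); ML with normal critical values gave 6.0–7.4%. REML with Satterthwaite t gave 4.8–5.3% throughout. Simulation error is about 0.15–0.2 percentage points.

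**3. Effect size.** The arm sizes in the pooled-SD formula are fixed, so the SD scales with the standard errors. In the random-intercept simulations the SD rebuilt from arm-specific model standard errors under ML was 0.952–0.965 of its REML value. Taking the numerator as unchanged, inflation is 1/0.965 = 1.036 to 1/0.952 = 1.050. An effect of 0.80, the plan's threshold for large, would read 0.80/0.965 = 0.83 to 0.80/0.952 = 0.84.

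**4. Identity residual matrix, no subject effect.** With complete data, p fixed effects and common within-person correlation ρ, the ratio of the ML interaction standard error to the true one is √[((72 − p)/72)/(1 − ρ)]. For p = 4 and ρ = 0.5 this is √(0.944/0.5) = 1.37, so the standard error is too large. The ratio exceeds 1 once ρ > p/72, that is 0.06 for p = 4 or 0.08 for p = 6. Simulated type I error under ML, across the scenarios run:

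| ρ | Type I error |
|---|---|
| 0 | 5.4–5.8% |
| 0.3 | 2.4–3.0% |
| 0.5 | 0.8–1.4% |
| 0.7 | 0.1–0.4% |

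For ρ of 0.3 to 0.7 the standard error is 12–76% too large. REML moves the test further the same way: at ρ = 0.3, linear, complete data, 2.4% becomes 2.1%.

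**The case against.** The strongest objection concerns direction. A reader might infer that every group-by-time test, including the primary ISI test, is run above 5%. The document does not support that. It names no random intercept or slope, and identity may describe the residual matrix alone. On that reading the interaction test is conservative, and the unmodelled correlation far outweighs the ML bias. This objection stands, and it makes the point conditional. It does not clear the plan: such a model has no subject effect although it is presented as a mixed model for repeated measures, and once the correlation is modelled the ML bias is what remains.

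Second, ML is legitimate for comparing likelihoods of models that differ in fixed effects, such as those with and without the quadratic term. That stands too, though it does not justify ML for the final estimates. The plan does not say which test decided whether the quadratic term stayed.

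Third, maximum likelihood may be loose wording for REML. The text does not rule this out; if so, it needs correcting.

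Fourth, the shift is small for a 24-person pilot. That is right: it would alter a significance statement only for p-values close to 0.05. A reader might also infer that the bias is always worse under an unstructured covariance than under a random intercept. The figures do not show this: with quadratic time and complete data both give an SE ratio of 0.957.

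**Conclusion.** The point holds in conditional form, and the effect is modest. If within-person correlation is modelled, ML as stated gives a group-by-time standard error about 2–5% too small, type I error of about 5.5–6.6% with t-based degrees of freedom (up to about 7.4% with normal critical values), and standardized effects about 4–5% too large. The effect-size figure also requires that the standard errors in the SD formula come from the model, which the plan leaves open.

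If identity means independent residuals with no subject effect, the interaction test errs in the opposite direction, and that is the larger fault. The documents do not establish which model was fitted, so neither an inflated nor a conservative primary test can be asserted outright. They also do not show that any particular result would change. The sizes rest on the assumptions listed with the calculations, including that ISI completion resembles diary completion in the missing-data case.

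**What to change.** 1. State the estimator, the random effects, what sigma refers to, the degrees-of-freedom method, and which standard errors enter the SD formula.
2. Make sure the model represents within-person correlation, for example with a subject random intercept. If the fitted model does not, correct this first.
3. Report final models by REML with Satterthwaite degrees of freedom, or Kenward-Roger where the software offers it. Keep ML only for likelihood comparisons between models with different fixed effects.
4. Recompute standard errors, p-values and standardized effect sizes from the REML fit.

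The cost is rerunning the models, since the section describes completed analyses, and revising the text. Where within-person correlation is already modelled, p-values and effect sizes become slightly less favourable. No new data are needed.
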